9.2 Discussion of Study Design

Study 270-303 is a Phase 3b, single arm, open-label study designed to assess whether BMN 270, at a dose of 6E13 vg/kg with prophylactic corticosteroids, can safely and effectively improve the FVIII activity profiles and alter the clinical phenotype of hemophilia A patients with residual FVIII activity \leq 1 IU/dL. Subjects must have high-quality, well-documented historical data available concerning previous bleeding episodes and exogenous FVIII usage over the previous 12 months in order to be eligible to enroll in the study.

Given that BMN 270 is likely a one-time treatment, due to antibody formation against the AAV5 capsid post-infusion, and the well-characterized clinical experience of patients with severe hemophilia A on currently available chronic therapies, having a separate control group in this study was deemed to be inappropriate and unnecessary, as has been the case with all AAV gene therapy trials to date.

Approximately 20 adult subjects with severe HA will receive a 6E13 vg/kg dose of BMN 270 as a single intravenous infusion in conjunction with receipt of a prophylactic corticosteroid regimen. Post-infusion, subjects will be eligible to receive reactive corticosteroids, as indicated.

9.3 Selection of Study Population

Approximately 20 adult hemophilia A patients with residual FVIII levels \leq 1 IU/dL may enroll into the study.

Additional criteria for participation in the study are provided in Section 9.3.1 and Section 9.3.2.

9.3.1 Inclusion Criteria

Individuals eligible to participate in this study must meet all of the following inclusion criteria:

1. Males \geq 18 years of age with hemophilia A and residual FVIII levels \leq 1 IU/dL as evidenced by medical history, at the time of signing the informed consent.
2. Must have been on prophylactic hemophilia therapy for at least 12 months prior to study entry. High-quality, well-documented historical data concerning bleeding episodes and hemophilia therapy usage over the previous 12 months must be available.
3. Treated/exposed to FVIII concentrates or cryoprecipitate for a minimum of 150 exposure days (EDs).

4. Willing and able to provide written, signed informed consent after the nature of the study has been explained and prior to any study-related procedures.
5. No previous documented history of a detectable FVIII inhibitor, and results from a Bethesda assay or Bethesda assay with Nijmegen modification of less than 0.6 Bethesda Units (BU) (or less than 1.0 BU for laboratories with a historical lower sensitivity cutoff for inhibitor detection of 1.0 BU) on 2 consecutive occasions at least one week apart within the past 12 months (at least one of which should be tested at the central laboratory).
6. Sexually active participants must agree to use an acceptable method of effective contraception, either double-barrier contraception (ie, condom + diaphragm; or condom or diaphragm + spermicidal gel or foam) or their female partner either using hormonal contraceptives or having an intrauterine device. Participants must agree to contraception use for at least 12 weeks post-infusion; after 12 weeks, subjects may stop contraception use only if they have had 3 consecutive semen samples with viral vector DNA below the limit of detection.
7. Willing to abstain from alcohol consumption for at least the first 52 weeks following BMN 270 infusion.

9.3.2 Exclusion Criteria

Individuals who meet any of the following exclusion criteria will not be eligible to participate in the study:

1. Subjects with detectable pre-existing antibodies to the AAV5 capsid are excluded with the following exception: up to 25% of subjects may have detectable pre-existing AAV5 capsid antibodies with titer level below the minimum required dilution (< 20).
2. Any evidence of active infection, including COVID-19, or any immunosuppressive disorder, except for HIV infection. HIV-positive patients who meet all other eligibility criteria may be included if they have a CD4 count > 200/mm³ and an undetectable viral load (unquantifiable viral load as defined as less than the limit of quantification by the testing laboratory's assay is permitted) while receiving an antiretroviral therapy (ART) regimen that does not contain efavirenz or another potentially hepatotoxic ART.
3. Significant liver dysfunction with any of the following abnormal laboratory results:
 - ALT (alanine aminotransferase) > 1.25x ULN;
 - AST (aspartate aminotransferase) > 1.25x ULN;
 - GGT (gamma-glutamyltransferase) > 1.25x ULN;
 - Total bilirubin > 1.25x ULN;
 - Alkaline phosphatase > 1.25x ULN; or

- INR (international normalized ratio) ≥ 1.4 .

Subjects whose liver laboratory assessments fall outside of these ranges may undergo repeat testing of the entire liver test panel within the same Screening window and, if eligibility criteria are met on retest, may be enrolled after confirmation by the Medical Monitor.

4. FibroScan or prior liver biopsy showing significant fibrosis of 3 or 4 as rated on a scale of 0-4 on the Batts-Ludwig ([Batts 1995](#)) or METAVIR ([Bedossa 1996](#)) scoring systems, or an equivalent grade of fibrosis if an alternative scale is used.
5. Evidence of any bleeding disorder not related to hemophilia A.
6. Platelet count of $< 100 \times 10^9/L$.
7. Creatinine $\geq 1.5 \text{ mg/dL}$.
8. Liver cirrhosis or other clinically significant liver disease of any etiology as assessed by FibroScan or liver ultrasound.
9. Chronic or active hepatitis B as evidenced by positive serology testing (hepatitis B surface antigen [HBsAg], hepatitis B surface antibody [HBsAb], and hepatitis B core antibody [HBcAb]) and confirmatory HBV DNA testing. Refer to the Centers for Disease Control (CDC) table for the interpretation of serological test results in the Laboratory Manual.
10. Active Hepatitis C as evidenced by detectable HCV RNA or currently on antiviral therapy.
11. Active malignancy, except non-melanoma skin cancer.
12. History of hepatic malignancy.
13. History of arterial or venous thromboembolic events (eg, deep vein thrombosis, non-hemorrhagic stroke, pulmonary embolism, myocardial infarction, arterial embolus), with the exception of catheter-associated thrombosis for which anti-thrombotic treatment is not currently ongoing.
14. Known inherited or acquired thrombophilia, including conditions associated with increased thromboembolic risk, such as atrial fibrillation.
15. Treatment with any investigational product within 30 days or 5 half-lives of the investigational product prior to the screening period. For subjects who have received a prior investigational product, all ongoing adverse events (AEs) experienced while receiving that investigational product must have resolved prior to screening for this study.

16. Any condition that, in the opinion of the Investigator or Sponsor would prevent the patient from fully complying with the requirements of the study (including possible corticosteroid treatment and/or use of alternative immunosuppressive agents outlined in the protocol) and/or would impact or interfere with evaluation and interpretation of subject safety or efficacy result.
17. Prior treatment with any vector or gene transfer agent.
18. Major surgery planned in the 52-week period following the infusion with BMN 270.
19. Use of systemic immunosuppressive agents, not including corticosteroids, or live vaccines within 30 days before the BMN 270 infusion.
20. Concurrent enrollment in another clinical study, unless it is an observational (non-interventional) clinical study that does not interfere with the requirements of the current protocol or have the potential to impact the evaluation of efficacy and safety of BMN 270 and with prior consultation with the Medical Monitor.
21. Known allergy or hypersensitivity to BMN 270 investigational product formulation.
22. Unwilling to receive blood or blood products for treatment of an adverse event and/or a bleeding episode.

9.3.2.1 Optional Liver Biopsy Inclusion and Exclusion Criteria

Individuals eligible for the optional liver biopsy must meet the following inclusion criterion:

1. Able to sign informed consent and comply with requirements for the optional liver biopsy
2. Documentation of FVIII activity ≥ 50 IU/dL (or higher, depending on local guidelines and/or Investigator discretion) within 24 hours prior to the liver biopsy being performed (FVIII activity levels should be assessed at the local laboratory). Subjects may be treated with additional exogenous FVIII replacement products in order to increase their FVIII levels activity to an appropriate level, under the supervision/instruction of the Investigator.

Individuals who meet any of the following exclusion criteria will not be eligible for the optional liver biopsy:

1. Any condition that, in the opinion of the Investigator or a hepatologist/radiologist would make liver biopsy contraindicated. This includes (but is not limited to) abnormalities detected on liver ultrasound performed within 28 days of procedure, or prior liver ultrasound result within 90 days that would preclude safe performance of the biopsy.

9.3.3 Removal of Subjects from Treatment or Assessment

Subjects may withdraw their consent to participate in the study at any time without prejudice. The Investigator must withdraw from the study any subject who requests to be withdrawn.

Such subjects will always be asked about the reason(s) for withdrawal. The Investigator will discuss with the subject appropriate procedures for withdrawal from the study. The Investigator should ask the subject's consent to perform the procedures listed under the early termination visit. Should a subject withdraw from the study, all efforts will be made to complete and report the observations as thoroughly as possible up to the date of the withdrawal.

A subject's participation in the study may be discontinued at any time at the discretion of BioMarin or of the Investigator and in accordance with his/her clinical judgment. When possible, the tests and evaluations listed for the termination visit should be carried out and every effort will be made to gather follow-up safety data if possible.

BioMarin must be notified of all subject withdrawals as soon as possible. BioMarin also reserves the right to discontinue the study at any time for either clinical or administrative reasons and to discontinue participation by an individual Investigator or site for poor enrollment or noncompliance.

Reasons for which the Investigator or BioMarin may withdraw a subject from the study include, but are not limited to, the following:

- Subject requires medication or medical procedure prohibited by the protocol
- Subject does not adhere to study requirements specified in the protocol
- Subject was erroneously enrolled into the study or does not meet entry criteria and not yet been dosed with BMN 270; subjects who do not meet entry criteria but who erroneously receive BMN 270 should remain in the study for safety monitoring
- Subject is lost to follow-up

If a subject fails to return for scheduled visits, a documented effort must be made to determine the reason. If the subject cannot be reached by telephone, a certified letter should be sent to the subject requesting contact with the Investigator. This information should be recorded in the study records.

Subjects may be considered lost to follow-up if the subject has missed 3 consecutive visits in the study and has failed to communicate a reason for this to the site. In addition, the site has documented at least 4 attempted contacts by key research personnel to reach the subject without success in the following manner:

- 2 attempts by telephone or email (if possible); then
- If telephone/email contacts are unsuccessful, 2 attempts must be made by certified letter or by appropriate local process.

Where communication has been made by phone, this should be documented in the subject source notes.

The Investigator or designee must explain to each subject, before enrollment into the study, that for evaluation of study results, the subject's protected health information obtained during the study may be shared with the study Sponsor, regulatory agencies, and IRB/IEC. It is the Investigator's (or designee's) responsibility to obtain written permission to use protected health information per country-specific regulations, such as the Health Insurance Portability and Accountability Act (HIPAA) in the US, from each subject. If permission to use protected health information is withdrawn, it is the Investigator's responsibility to obtain a written request, to ensure that no further data will be collected from the subject and the subject will be removed from the study.

9.3.3.1 Study Safety Evaluation Criteria

If any of the following events occur in a subject in the study who has received BMN 270 infusion, an urgent evaluation by the DMC will be required and further enrollment into the trial will be temporarily put on hold if recommended by the DMC per Section 9.1.

1. Liver dysfunction (criteria do not apply to ALT elevations with an extra-hepatic etiology):
 - ALT > 5x ULN, for more than 2 weeks
 - ALT > 3x ULN **and** (total bilirubin > 2x ULN **or** INR >1.5)
 - ALT > 3x ULN with signs and symptoms of liver dysfunction
2. The occurrence of Grade 4 or Grade 5 adverse events assessed as related to study drug (events of liver dysfunction are defined above).
3. The occurrence of an AE of hepatic failure.
4. The detection of high-titer neutralizing antibodies (>5 BU) to hFVIII following BMN 270 infusion in two subjects.
5. The occurrence of any cancer (except non-melanoma skin cancer) at any point after BMN 270 infusion.
6. The occurrence of a thromboembolic event with FVIII activity > 150 IU/dL in one subject.

If any of the following events occurs in a subject in the study who has received BMN 270 infusion, an urgent evaluation by the DMC will be required. Further enrollment into the trial will continue while DMC evaluation is ongoing, unless deemed otherwise by the DMC:

1. The detection of high-titer neutralizing antibodies (>5 BU) to hFVIII following BMN 270 infusion in one subject.

2. Occurrence of a thromboembolic event in one subject.

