ALT \geq 1.5x Baseline or $>$ ULN	
 Repeat LTs and FVIII within 24-72 hours Continue to monitor LTs until ALT is stable or not increasing Investigate for alternative etiologies (eg, concomitant medications, viral or autoimmune hepatitis, alcohol use, recreational drug use, special diets, strenuous exercise, prior and/or concurrent illnesses, exposure to environmental and/or industrial chemicals, etc.) If no alternative etiology is found, initiate reactive corticosteroids with the following tapering schedule: 60 mg x 2 weeks; 40 mg x 3 weeks; 30 mg x 1 week; 20 mg x 1 week; 10 mg x 1 week upon consultation with the Medical Monitor Consider evaluation with additional liver tests (including but not limited to ALT, AST, bilirubin, and alkaline phosphatase) Consider obtaining other possibly relevant laboratory evaluations (albumin, PT/INR, CRP, etc.) Consider obtaining complete blood count with differential to assess for eosinophilia Consider obtaining PBMC, C3, C3a, Bb, and sC5b-9 to evaluate potential immune response (prior to starting reactive oral corticosteroids) Continue to taper as long as subject's ALT is not increasing. Decisions regarding regimen modification may be made based upon Investigator judgement and discussion with the Medical Monitor For any ALT elevations that begin after 52 weeks on study, please consult the Medical Monitor prior to initiating corticosteroids unless there is an imminent safety concern
Worsening ALT	
If after 2 weeks ALT levels have worsened with corticosteroid dose of 60 mg/day, the following is recommended:
 
 Investigate for alternative etiologies including labs noted above, if not previously checked Increase corticosteroid dose up to a maximum of 1.2 mg/kg for no more than 2 weeks For subjects who are refractory to the maximum dose of corticosteroids, or intolerant to use of corticosteroids, consider use of alternative immunosuppressants (tacrolimus or mycophenolate) Consider gastroenterology and/or hepatology consult, abdominal workup, imaging (including MRI or ultrasound), and/or liver biopsy as appropriate 
Any concerns should be discussed between the Investigator and the Medical Monitor

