9.7.8.4 Liver and Hepatitis Testing

Subjects will be screened for evidence of previous or active hepatitis B or hepatitis C infection at Screening; hepatitis B screening should include HBsAg, HBsAb, and HBcAb. Subjects with documented results showing an absence of active hepatitis B or hepatitis C infection (as measured by negative surface antigen or DNA for hepatitis B or negative RNA testing for hepatitis C) 30 days prior to providing signed informed consent do not need to repeat those tests during the screening period.

Evidence of ongoing hepatitis B or hepatitis C infection is exclusionary. Subjects with a history of hepatitis B or hepatitis C infection prior to study entry will be tested for hepatitis B and hepatitis C reactivation at the timepoints listed in [Table 9.1.6](#). Subjects with a history of hepatitis B or hepatitis C will be asked for information about the treatments received as part of their medical history assessment at Screening.

A liver ultrasound, fasting FibroTest, and liver tests (LTs) during Screening will be performed to assess for clinically significant liver disease and HCC. A FibroScan may also

be performed during Screening at the discretion of the Investigator. Fasting FibroTest results must be available prior to BMN 270 infusion.

Where a biopsy has been taken for safety-related reasons or was available from a past procedure, the Sponsor may request the biopsy information to help evaluate the impact of BMN 270 on the liver. The Sponsor may request that slides from a liver biopsy be made available for additional histopathological review.

LTs will be monitored on a regular basis; at each time point, the following LTs should be assessed:

Table 9.7.8.4.1: Liver Tests

Liver Tests (LTs)			
Alkaline Phosphatase	AST (SGOT)	Total Bilirubin	LDH
ALT (SGPT)	Direct Bilirubin	GGT	

ALT, alanine aminotransferase; AST, aspartate aminotransferase; GGT, gamma-glutamyltransferase; LDH, lactate dehydrogenase; SGOT, serum glutamic-oxaloacetic transaminase; SGPT, serum glutamic-pyruvic transaminase

Elevated ALT levels (above the upper limit of normal range) should be evaluated according to the plan outlined in [Table 9.4.8.2.2.1](#) (note that these evaluations may indicate additional testing of LTs and FVIII levels at unscheduled visits; these unscheduled laboratory tests may be completed by a mobile nursing professional at sites where the use of MN services has been approved).

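### The DMC liver trigger on INR has no required INR behind it: a site following the protocol can have ALT above 3x ULN and no coagulation result to judge it by

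*Protocol*

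**What the plan says.** Section 9.3.3.1 lists events that require urgent DMC evaluation, with enrollment held if the DMC recommends it. One of the three liver-dysfunction criteria is "ALT > 3x ULN and (total bilirubin > 2x ULN or INR >1.5"). The other two are ALT above 5x ULN for more than two weeks, and ALT above 3x ULN with signs and symptoms of liver dysfunction. ALT elevations of extra-hepatic origin are excluded.

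Section 9.7.8.4 fixes the liver panel: "LTs will be monitored on a regular basis; at each time point, the following LTs should be assessed". Table 9.7.8.4.1 then lists alkaline phosphatase, AST, total bilirubin, LDH, ALT, direct bilirubin and GGT. PT/INR appears instead in the coagulation screen of Table 9.7.8.2.1.

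Section 9.7.8.4 sends any ALT above ULN to Table 9.4.8.2.2.1. The first row of that table applies from 1.5x baseline or above ULN. It instructs "Repeat LTs and FVIII within 24-72 hours" and "Continue to monitor LTs until ALT is stable or not increasing", and on PT/INR it says "Consider obtaining other possibly relevant laboratory evaluations (albumin, PT/INR, CRP, etc".) The next row opens "If after 2 weeks ALT levels have worsened with corticosteroid dose of 60 mg/day, the following is recommended" and includes "Investigate for alternative etiologies including labs noted above, if not previously checked".

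**The concern.** Once the event is known, DMC evaluation is mandatory. The measurement that reveals the event is optional. The trigger makes INR an alternative to bilirubin, so it is there to catch subjects whose bilirubin has not crossed its limit. Those are the subjects in whom the trigger cannot be judged unless an INR is drawn.

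If the gap is real, a site can follow every instruction and still miss an event that Section 9.3.3.1 says must go urgently to the DMC. What is at stake is subject safety and the decision to go on enrolling. The efficacy analysis is not affected.

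**Working it through.** The protocol gives no figure to reproduce here. The check is whether any current instruction guarantees an INR when ALT exceeds 3x ULN, and how far apart the scheduled ones are.

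**Scheduled liver tests, Year 1** (Sections 12.5.1 and 12.6.1)
- Weekly, Weeks 1-26: 26 visits.
- Weeks 28, 30, 32, 34, 36, 40, 44, 48, 50, 52: 10 visits.
- Total: 26 + 10 = 36.

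**Scheduled coagulation screens, Year 1** (Sections 12.5.11 and 12.6.6)
- Weeks 4, 16, 26: 3.
- Weeks 32, 36, 44, 52: 4.
- Total: 3 + 4 = 7. All coincide with liver-test visits.

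**Liver-test visits with no scheduled INR**

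| Period | Visits |
|---|---|
| Weeks 1-3 | 3 |
| Weeks 5-15 | 11 |
| Weeks 17-25 | 9 |
| Weeks 28, 30, 34, 40, 48, 50 | 6 |
| Total | 29 |

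Check: 29 + 7 = 36, and 29/36 = 81%. The longest Year 1 intervals between scheduled INRs are 16 - 4 = 12 weeks and 26 - 16 = 10 weeks. In Years 2-5 (Section 12.7.2) coagulation is scheduled at Weeks 76, 104, 128, 156, 180, 208, 232 and 260, so the intervals alternate between 24 and 28 weeks.

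**Where the Year 1 gaps fall.** The suggested prophylactic taper in Table 9.1.6 runs over Weeks 9-19, and Week 16 is the only one of those 11 weeks with a scheduled INR. Section 7.4 reports that in study 270-201, under a different steroid regimen, ALT generally rose during the taper.

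**What an ALT rise adds**
1. The 24-72 hour repeat covers liver tests and FVIII. By Table 9.7.8.4.1 that excludes INR.
2. The first row makes PT/INR something to consider, with no threshold at which it becomes required.
3. The Worsening ALT row recommends the earlier labs if they have not been checked. If reactive steroids start at the repeat, the earliest this can act is 1-3 days + 14 days = day 15-17 after the first elevated result, and only if ALT has worsened. It does not reach a subject whose ALT stays above 3x ULN but is stable or falling.
4. Unscheduled local labs (Section 9.7.8.2) are at the investigator's discretion.
5. The Hy's law item among the events of special interest (Section 10.2.1) uses transaminases and bilirubin only.

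No step guarantees an INR. The INR criterion can go unassessed in a subject with all of the following: ALT above 3x ULN of hepatic origin, bilirubin at or below 2x ULN, no signs or symptoms of liver dysfunction, ALT not above 5x ULN for more than two weeks, and no coagulation draw due.

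**The case against.** The strongest reply is that this is a matter of clinical judgment already provided for. PT/INR is named in the first row of the table, well below 3x ULN, so a compliant site must think about it at the first elevation. Reactive steroids are started in consultation with the Medical Monitor. Every ALT above ULN is reported within 24 hours as an event of special interest, and the DMC reviews safety data on an ongoing basis. An INR goes undrawn only if someone who knows about the ALT decides against it. The day 15-17 figure describes one row and is not a delay the table imposes.

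The protocol also accepts discretionary testing behind other triggers. The inhibitor assay is run as the sponsor sees fit, and D-dimer is optional. Subjects enter with INR below 1.4, and Section 7.4 reports no Hy's law events among 151 treated subjects. One INR at the confirmatory draw might be enough.

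Much of this stands: the prompt comes early, the safeguards are real, and no harm can be sized. However, the safeguards show the ALT rise and do not supply an INR that was not drawn. Discretion elsewhere in the list does not make this criterion assessable. A single normal INR does not settle the matter either, because the criterion remains live for as long as ALT is above 3x ULN.

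**Conclusion.** The concern holds. The current protocol sets a mandatory DMC trigger on INR and nowhere requires the INR at the trigger's own ALT threshold. In Year 1, 29 of 36 scheduled liver-test visits carry no INR, and the longest interval between scheduled INRs is 12 weeks. These counts describe the schedule of draws and say nothing about risk.

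The gap is confined to the INR alternative. With about 20 subjects planned, the affected group is small, cannot be estimated from the document, and could be zero. The conclusion rests on reading the table's wording as written (an item to consider is not a requirement) and, for the day 15-17 figure, on reactive steroids starting at the repeat draw. The change is worth making because it is cheap and makes a stated safety rule workable. The point does not call the design into question.

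**What to change.** In Table 9.4.8.2.2.1, require PT/INR whenever ALT is above 3x ULN: at the 24-72 hour repeat and at each later liver-test draw while ALT remains above that level. This includes the case where ALT first crosses 3x ULN later in an episode. Exempt elevations with an established extra-hepatic cause, to match Section 9.3.3.1. Leave the other optional items as they are.

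The cost is one changed line and one added coagulation tube at draws already due. As an illustration, the recommended reactive course starts "60 mg x 2 weeks; 40 mg x 3 weeks; 30 mg x 1 week" and then gives one week each at 20 mg and 10 mg, so it lasts 2 + 3 + 1 + 1 + 1 = 8 weeks. If ALT stayed above 3x ULN throughout with weekly liver tests, that would be at most 1 + 8 = 9 tubes, fewer where a scheduled coagulation draw coincides. Subjects whose ALT never exceeds 3x ULN incur nothing.

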WPAI+CIQ:HS	Work Productivity and Activity Impairment plus Classroom Impairment Questions: Hemophilia Specific

Definition of Terms:**Investigational Product (IP):**

“A pharmaceutical form of an active ingredient or placebo being tested or used as a reference in a clinical trial, including a product with a marketing authorization when used or assembled (formulated or packaged) in a way different from the approved form, or when used for an unapproved indication, or when used to gain further information about an approved use” (from International Conference on Harmonisation of Technical Requirements for Registration of Pharmaceuticals for Human Use ICH Harmonised Tripartite Guideline: Guideline for Good Clinical Practice E6 [ICH E6 (R2)]).

The terms “IP” and “study drug” may be used interchangeably in the protocol.

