The current data available has shown an established positive benefit:risk profile for BMN 270 at the 6E13 vg/kg dosing level, although the impact of prophylactic corticosteroids requires further investigation. Given the monitoring measures in place in the clinical protocol(s) to minimize the risk to subjects participating in the existing studies, the identified risks are justified by the anticipated benefits that may be afforded to subjects. Each subject in 270-303 will have a comprehensive surveillance plan that monitors LTs during the study, and elevations in LTs will be addressed according to the guidelines set forth in the protocol. Safety will be assessed by adverse event reporting and clinical laboratory assessments.

For additional information on the risks and benefits of treatment with BMN 270, refer to the current version of the Investigator's Brochure.

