8 STUDY OBJECTIVES

The primary efficacy objective of the study is to:

- Assess the efficacy of BMN 270 with prophylactic corticosteroids defined as FVIII activity, as measured by chromogenic substrate assay, during Weeks 49-52 following intravenous infusion of BMN 270

The secondary efficacy objectives of the study are to:

- Assess the impact of BMN 270 with prophylactic corticosteroids on the use of exogenous FVIII replacement therapy from Week 5 to last visit by data cutoff (for Week 52 analysis) for subjects receiving prior FVIII prophylaxis or on use of emicizumab from Week 27 to last visit by data cutoff (for Week 52 analysis) for subjects receiving prior emicizumab prophylaxis
- Assess the impact of BMN 270 with prophylactic corticosteroids on the number of bleeding episodes requiring exogenous FVIII replacement therapy from Week 5 to last visit by data cutoff (for Week 52 analysis) for subjects receiving prior FVIII prophylaxis or on use of emicizumab from Week 27 to last visit by data cutoff (for Week 52 analysis) for subjects receiving prior emicizumab prophylaxis
- Assess the impact of BMN 270 with prophylactic corticosteroids on quality of life as measured by the Haemo-QoL-A questionnaire at Week 52 of the study compared to baseline

The tertiary efficacy objective of the study is to:

- Assess the impact of BMN 270 with prophylactic corticosteroids on patient-reported outcomes (PROs) (other than Haemo-QoL-A) at Week 52 of the study compared to baseline

The exploratory efficacy objective of the study is to:

- Assess the efficacy of BMN 270 with prophylactic corticosteroids defined as FVIII activity, as measured by chromogenic substrate assay, during Weeks 49-52, following intravenous infusion of BMN 270 for subjects with detectable AAV5 total antibodies below the minimum required dilution at Screening

The safety objectives of the study are to:

- Evaluate the short-term safety of BMN 270 with prophylactic corticosteroids following intravenous infusion
- Assess the long-term safety of BMN 270 with prophylactic corticosteroids

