9.4.8.2.1 Prophylactic Corticosteroids

All subjects will be started on prophylactic corticosteroids starting on the day of infusion (Day 1). The first dose of prophylactic corticosteroids (40 mg of prednisone or prednisolone, or an equivalent dose of another corticosteroid) should be taken at least 3 hours prior to the start of the BMN 270 infusion and continued on a daily basis. [Table 9.1.6](#) provides the recommended prophylactic corticosteroid course, including taper and post-corticosteroid additional monitoring of FVIII activity, LTs, and hepatitis B/hepatitis C reactivation. Clinical judgment, weighing the potential risks and benefits of corticosteroid treatment, should always be exercised when considering adjustment of corticosteroid doses. Discussions between the Investigator and Medical Monitor are advised for any questions or concerns.

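### The urgent DMC trigger for Grade 4/5 events covers only those attributed to BMN 270, not those attributed solely to the corticosteroids or other immunosuppressants given with it

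*Protocol*

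**What the plan says.** Section 9.3.3.1 (Study Safety Evaluation Criteria) contains two lists, and any event on either requires an urgent DMC evaluation. The first has six items: liver dysfunction, certain Grade 4/5 events, hepatic failure, high-titer inhibitors in two subjects, cancer, and thromboembolism with FVIII activity above 150 IU/dL. The second has two: high-titer inhibitors in one subject, and "Occurrence of a thromboembolic event in one subject". The Grade 4/5 item reads "The occurrence of Grade 4 or Grade 5 adverse events assessed as related to study drug".

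Section 4 says that the terms IP and study drug "may be used interchangeably in the protocol", and the synopsis gives the investigational product as a single infusion of BMN 270.

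The regimen under study is wider. One safety objective in section 8 is to "Assess the long-term safety of BMN 270 with prophylactic corticosteroids"; the short-term objective names the same combination. Section 7.4 calls the benefit-risk profile at this dose positive, "although the impact of prophylactic corticosteroids requires further investigation". Under 9.4.8.2.1 every subject takes the first steroid dose at least 3 hours before the infusion. Sections 10.3.3 and 10.3.3.3 have the investigator judge each adverse event against study drug, corticosteroids and other immunosuppressants.

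**The concern.** The trial adds a planned 19-week steroid course to a vector already given in earlier studies, and the protocol itself says that the effect of this addition is not settled. The urgent trigger for the most severe adverse events nevertheless depends on attribution to the vector alone. If an investigator attributes a fatal infection to prednisone and not to BMN 270, item 2 is not met. The same infection attributed to BMN 270 meets it.

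What is at stake is how soon the independent committee must look. A life-threatening steroid complication could be a reason to change the prophylactic regimen for subjects still on it and for those not yet dosed. It deserves the same speed as an event attributed to the vector.

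**Working it through.** The protocol states no figure on this point, so the check is a comparison of texts.

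**Step 1: what study drug means.** Section 4 equates it with the investigational product. The synopsis identifies that product as BMN 270. Sections 10.3.3 and 10.3.3.3 name corticosteroids and other immunosuppressants beside study drug as separate possible causes. Item 2 therefore cannot naturally be read to include them.

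**Step 2: who is exposed, and to how much.** All of the approximately 20 subjects. Table 9.1.6 starts at 40 mg/day and tapers to 5 mg/day in Week 19. Section 9.4.8.2.2 adds reactive courses starting at 60 mg/day. Table 9.4.8.2.2.1 allows up to 1.2 mg/kg for at most 2 weeks, and tacrolimus or mycophenolate if steroids fail or are not tolerated.

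**Step 3: whether another item closes the gap.** Take a Grade 4/5 infection or gastric ulcer attributed only to steroids.

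| Item in 9.3.3.1 | Event | Limit by cause | Met? |
|---|---|---|---|
| List 1, item 1 | Liver dysfunction by laboratory values or signs | ALT rises of extra-hepatic etiology excluded | No, unless the liver criteria are also met |
| List 1, item 2 | Grade 4/5 adverse event | Related to study drug | No |
| List 1, item 3 | Hepatic failure | None | No |
| List 1, item 4 | High-titer inhibitor, two subjects | None | No |
| List 1, item 5 | Cancer other than non-melanoma skin cancer | None | No |
| List 1, item 6 | Thromboembolism with FVIII above 150 IU/dL | None | No |
| List 2, item 1 | High-titer inhibitor, one subject | None | No |
| List 2, item 2 | Thromboembolism, one subject | None | No |

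One of the six list 1 items carries a study-drug relatedness condition. Item 1 also has a limit by cause, but of a different kind.

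**Step 4: the complications that the protocol names.** Section 9.4.8.2.2 mentions five in connection with steroid therapy: glucose intolerance, hyperlipidemia, gastric ulcers, osteoporosis and infections. None of the five is an event in the other seven items. They are named as things to evaluate or prevent, not as expected Grade 4/5 events, so only infection and gastric ulcer serve as examples here.

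**Step 5: what still happens to such an event.** Grade 4 and 5 events are always SAEs (Table 10.3.3.2.1). They go to the sponsor within 24 hours whatever the attribution (10.5.1). The sponsor promptly evaluates every SAE regardless of the investigator's causality assessment (10.3.3.3). The DMC reviews individual safety data on an ongoing basis (15) and may pause enrolment (9.1). None of these provisions requires an urgent DMC evaluation.

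**The case against.** The strongest reply is that this is a defensible design choice. The vector is given once and cannot be withdrawn, while the steroid dose can be adjusted by clinical judgment (Table 9.1.6, 9.4.8.2.1) and replaced by other agents if it is not tolerated. Every subject is screened for steroid eligibility before dosing (9.4.8.2). Nothing in the protocol promises urgent DMC review of steroid-only events. Section 7.4 reports no deaths and no discontinuations for adverse events among 151 dosed subjects.

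Much of this stands, and it keeps the severity low. It does not remove the point. Reversibility helps the individual subject after the event; it does not tell the committee sooner that the regimen may need changing. The earlier experience included steroids, but not this Day 1 prophylactic course, so it is indirect. Prompt SAE reporting applies equally to vector-related events, and the protocol still gives those an urgent trigger.

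A reader might also infer that list 1 leaves enrolment undefined while the DMC deliberates. The text does not support that. List 1 says that "further enrollment into the trial will be temporarily put on hold if recommended by the DMC per Section 9.1", which implies that enrolment continues until the DMC recommends otherwise. List 2 spells out the same arrangement: "Further enrollment into the trial will continue while DMC evaluation is ongoing, unless deemed otherwise by the DMC".

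**Conclusion.** The point holds as a narrow one. A Grade 4/5 event attributed only to corticosteroids or other immunosuppressants, and meeting no other listed criterion, does not require urgent DMC evaluation under the protocol, although those agents belong to the treatment whose safety is being assessed. This rests on reading study drug as section 4 defines it. It affects one of six list 1 items.

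Three stronger readings should be resisted:

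- A reader might infer that such an event goes unmonitored or can reach the DMC only at a routine meeting. Section 15 places meeting frequency and other committee functions in the DMC Charter and the SAP, which are not shown and may provide for ad hoc notification.
- A reader might infer that all the other triggers fire whatever the cause. Item 1 excludes ALT elevations of extra-hepatic etiology.
- A reader might want a probability of such an event in this trial. The documents give no rate, so none is offered.

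Severity is minor. The primary analysis is unaffected.

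**What to change.** Reword item 2 of the first list in 9.3.3.1 so that it covers Grade 4 or 5 adverse events assessed as related to study drug, to corticosteroids or to another immunosuppressive agent, in line with 10.3.3. If the DMC Charter repeats the trigger, give it the same wording.

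The change is one phrase. It needs no new data, because the investigator already records these attributions on the AE eCRF. The cost is possibly a few more urgent DMC reviews among about 20 subjects. The DMC keeps its discretion over enrolment.
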